# 1.3 Potential Risks & Benefits

# 1.3.1 Known Potential Risks

There are two categories of risk associated with this study:

### 1) The potential risks resulting from physical exercise.

Qualified, attending medical personnel will categorize the test outcomes (including post-test events) as one of the following, using the criteria that follow:

a) Benign events that fall within the "normal" set of outcomes for the tests;

*b)* "Abnormal" outcomes that do not, by themselves, warrant termination of the exercise and that do not cause the subject to stop exercise or complain; or

c) Adverse Events or Serious Adverse Events that are not "normal" outcomes, that warrant termination of the exercise, or that cause the subject to complain or terminate the exercise of their own volition.

In *Type c* events, the exercise will be immediately terminated. As needed, participants will receive on-site medical treatment, referral to hospital for immediate follow-up care, or a call will be placed for Emergency Medical Services (EMS), transport to hospital, and emergency treatment. Except where EMS are involved, the subject will be asked to stay at the testing lab for observation for at least half an hour after his or her condition is stable.

In all *Type c* cases, the research staff will attempt to contact the subjects' personal physician (or the person covering his or her practice, as available) by phone, to apprise him or her of the exercise outcome and the treatment given. Except where EMS are involved, this first phone call will be made after the subject is stable and before the subject leaves the testing lab. If no person-to-person contact can be made with the subject's physician (or their substitute) within this time frame, this fact will be documented and repeated attempts will be made and documented until contact is made.

Within 48 hours of the test, for both *Type b* and *Type c* events, the outcomes, treatments, and documentation of phone calls and other correspondence (e.g., with EMS) will be described in a written report to the subject's personal physician. The subject will also receive a copy of the report.

#### CONFIDENTIAL

This material is the property of the NYU School of Medicine and Langone Medical Center. Do not disclose or use except as authorized in writing by the study sponsor

Individuals experiencing Type a and Type b events will be supervised until their symptoms resolve. The event will be documented. Subsequent exercise sessions will be monitored to prevent recurrence of adverse event.

### **Criteria for Categorizing Exercise Adverse Events**

Type b Indications—"Abnormal" outcomes that do not, by themselves, warrant terminating the exercise test, such as occasional premature beats at rest and which are more frequent with exercise, or the appearance of a new but non-sustained arrhythmia.

Type c Indications—Adverse Events or Serious Adverse Events that should result in terminating the exercise.

Exercise Standards for Testing and Training from the American Heart Association will be used to define absolute and relative contra-indications to exercise testing [51].

### **Absolute Indications**

- Acute myocardial infarction (MI), within 2 days
- Ongoing unstable angina •
- Uncontrolled cardiac arrhythmia with hemodynamic compromise •
- Active endocarditis
- Symptomatic severe aortic stenosis •
- Decompensated heart failure •
- Acute pulmonary embolism, pulmonary infarction, or deep vein thrombosis •
- Acute myocarditis or pericarditis •
- Acute aortic dissection
- Physical disability that precludes safe and adequate testing •

#### **Relative Indications**

- Known obstructive left main coronary artery stenosis
- Moderate to severe aortic stenosis with uncertain relation to symptoms
- Tachyarrhythmia with uncontrolled ventricular rates •
- Acquired advanced or complete heart block
- Hypertrophic obstructive cardiomyopathy with severe resting gradient •
- Recent stroke or transient ischemic attack •
- Mental impairment with limited ability to cooperate •
- Resting hypertension with systolic or diastolic blood pressures >200/110 mm Hg •
- Uncorrected medical conditions, such as significant anemia, important electrolyte imbalance, and hyperthyroidism

Additionally, to minimize the risk of ulcer development in the "high risk" foot, we will inspect participants' feet weekly.

#### 2) Risks that are incurred by the performance of MR imaging. All subjects will be screened for the same potential hazards as routine clinical patients (see below) and those subjects at risk will not be imaged.

This research study involves the use of newly developed imaging hardware and software at 3T. The human subjects will be scanned using an FDA-approved 3.0 Tesla MRI scanner. A standard MRI safety form will be used for subject eligibility. All new technologies used in this investigation meet or surpass the safety standards of the FDA and are considered non-significant risk as defined in the "Guidance for Industry and FDA Staff – Criteria for Significant Risk Investigations of Magnetic Resonance Diagnostic Devices" issued July 14, 2003. According to the Blue Book memorandum entitled "Significant Risk and Non-significant Risk Medical Device Studies", magnetic resonance devices operating within FDA guidelines up to 8T are considered non-significant risk.

## 1.3.2 Known Potential Benefits

While there are no direct benefits to the patients for participating, the complete medical evaluation will be of general value since previously unknown medical problems may be detected. In addition, individuals who have diminished glucose regulation will be informed of these results, so that they can notify their personal physicians and have this monitored more closely. These individuals will be given advice on measures they can take to improve their peripheral glucose regulation, such as diet. Our licensed physical therapist will offer our subjects nutrition guidelines from the American Diabetes Association. The exercise tests may provide participants with information about their current state of health and physical fitness. The information may also be helpful in developing or altering an exercise program to enhance their physical fitness. The benefit to society will be the establishment of the efficacy of physical exercise on improving DPN symptoms, and by using advanced multinuclear MRI metrics to provide mechanistic insight into the exercise-associated adaptations in MV and metabolic functions.

**Risk/Benefit Assessment:** Although the potential benefits from participation in this study will be minimal for the individual subjects, the risks are minimal as well. In view of the potential benefits to society of establishment of the efficacy of physical exercise on improving DPN symptoms, the overall risk/benefit is favorable.

# 2 Objectives and Purpose

# 2.1 Primary Objective

The primary objective is to assess and compare the interventions (exercise versus control phase) in terms of the baseline to follow-up change in the following outcomes: 1) DTI, plasma ROS level, and the MNSI assessment of DPN symptoms (Aim 1); and 2) leg mitochondrial function, oxidative capacity (31P-MRI), peak MV response (BOLD-MRI), the proportion of fat-free muscle (IDEAL-MRI) and leg muscle strength (Aim 2).

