#### CONFIDENTIAL

This material is the property of the NYU School of Medicine and Langone Medical Center. Do not disclose or use except as authorized in writing by the study sponsor Behavioral Intervention Template Version: 5 MAY 2017 If a participant chooses to withdraw from the exercise intervention, they will be contacted by study personnel and reasons for withdrawal will be documented. We will seek written permission to contact participants and will reach them using their preferred method (phone or email). Reasons for withdrawal will be classified as related or unrelated to intervention. Participants will be invited to complete endpoint testing even if they choose to withdraw from the intervention.

Participants that cannot complete the study due to incompatible logistics (precipitating from i.e. covidrelated study suspension or personal leave of absence) will be encouraged to continue the study at a later date. Participants with long-term absences will be re-consented and will re-perform all study procedures in the longitudinal protocol described in section 6. Such participants will be considered newly enrolled and must meet all inclusion/exclusion criteria laid out in section 4. Long-term absence is defined as: 1) greater than 3-months between Step 2: Blood draw (section 6.4.1.2) and Post-non-exercise phase visit (section 6.4.3) or 2) greater than 4-months between Post-non-exercise phase visit (section 6.4.6).

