#### CONFIDENTIAL

conditions such as time of day and other risk factors. For the OGTT, samples are then collected at 30, 60, 90, and 120 minutes post glucose ingestion. We will compute the Matsuda whole body Index of Insulin Sensitivity (ISI) as follows and will be used at the insulin resistance (IR) variable:

 $ISI = \frac{10,000}{\sqrt{[fasting glucose x fasting insulin] x [mean glucose x mean insulin during OGTT]}}$ 

Baseline bloods obtained at time 0 will also be analyzed for measuring HgbA1C and C-reactive protein (CRP). In addition, we will use baseline bloods to estimate levels of hydrogen peroxide as a marker of ROS. None of these blood biomarkers will be used as an inclusion/exclusion criterion.

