# 9.3 Description of Statistical Methods

A weighted paired sample *t*-test will be used to assess whether each outcome changed from baseline to follow-up as a result of the exercise intervention. Weighted analysis of covariance (ANCOVA) will be used to compare the time points in terms of the change in each outcome. The change in each outcome from baseline to follow-up will be the dependent variable and the ANCOVA model will include the matching factors (age, baseline MNSI) and the measure of general activity level as numeric covariates and the binary indicator of intervention as a classification factor. The secondary objective is to assess the extent to which exercise induced improvements in DTI outcomes are mediated or explained by reduction in ROS. After testing the effect of the intervention on the change in DTI and the correlation between changes in DTI and ROS, an incomplete causal pathway meditational analysis will be conducted using the method of Baron and Kenny[63] with a bootstrap based test of the indirect (mediation) effect of ROS. The exploratory objective to identify baseline factors (e.g., age, MNSI, general activity) predictive of improvement, represented as the baseline to follow-up change in each outcome, will be addressed using linear regression and bivariate correlations. This analysis will be stratified by intervention and then conducted using data from both intervention groups combined. In each case, the assessment of compliance will be included as a weighting factor.

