# 9.3.2 Analysis of the Primary Efficacy Endpoint(s)

A matched-pairs Wilcoxon signed rank test will be applied to the within-subject change in each outcome among subjects demonstrating full compliance with the exercise program. Additionally, weighted analysis of covariance (ANCOVA) will be used to test the change in each outcome adjusting for the measured level of compliance using data from all subjects. The values of each outcome at

CONFIDENTIAL

baseline and follow-up for all subjects will be the dependent variable and the ANCOVA model will include time (baseline versus follow-up) as the within-subject factor of interest covariates, the measure of compliance as numeric covariate and an anonymized subject ID as a classification factor so that the comparison of times will be based on their within-subject difference. The secondary objective is to assess the extent to which exercise induced improvements in DTI outcomes are can be at least partially explained by reduction in ROS will be addressed using linear regression, The baseline to follow-up change in each outcome will be the dependent variable and the model will include the measure of compliance as a numeric factor and the within-subject change in ROS as the numeric factor of interest. A second regression will be conducted with baseline factors (e.g., age, MNSI, general activity) added to the model in order to identify factors predictive of improvement in each outcome.

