### 9.3.4 Adherence and Retention Analyses

The analysis will follow the intention-to-treat (ITT) principle and include data from every subject irrespective of whether the subject was compliant with the assigned intervention. A quantitative assessment of compliance with the intervention, ranging from 0 (complete non-compliance) to 1 (full compliance), will be included as a weighting factor to allow more compliant subjects to contribute more to the analysis. The weight for the control phase will be set to 1 since subjects are not required to exercise.

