# Attachments

These documents are relevant to the protocol, but they are not considered part of the protocol. They are stored and modified separately. As such, modifications to these documents do not require protocol amendments.

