# Attachment A

# Schedule of Events

Activity	Week 0	Week 1	Week 2	Week 3	Week 4	Week 5	Week 6	Week 7	Week 8	Week 9
Consent		Х								
MNSI	Х	Х								
Medical History	Х									
Height/Weight		Х					Х			
OGTT		Х								
Biweekly Health Assessment				х		Х				
VO 2 R Assessment							Х			
Plantar flexion training		Х								
Bloodwork		Х								
Actigraph**		Х	Х					Х	Х	
MRI		Х				Х				
Aerobic exercise								Х	Х	Х
Resistance exercise								Х	Х	Х
PROMIS								Х		
Calf muscle performance								Х		
9-item physical performance test								Х	Х	Х
Blood Pressure (BP)								Х	Х	Х

\*\*Actigraph to be worn for at least one week.

CONFIDENTIAL This material is the property of the NYU School of Medicine and Langone Medical Center. Do not disclose or use except as authorized in writing by the study sponsor Drug/Device Template Version: 13 JUN 2016

Page 2

# Attachment A Schedule of Events Cont....

Activity	Week 10	Week 11	Week 12	Week 13	Week 14	Week 15	Week 16	Week 17	Week 18
Consent									
MNSI									Х
Medical History									
Height/Weight								Х	
OGTT									Х
Biweekly Health Assessment									
VO 2 R Assessment								Х	
Plantar flexion training									
Bloodwork									Х
Actigraph						Х	Х		
MRI									Х
Aerobic exercise	Х	X	х	Х	х	Х	х		
Resistance exercise	Х	х	х	Х	х	Х	х		
PROMIS							х		
Calf muscle performance							х		
9-item physical performance test	X	X	X	X	X	х	X		
Blood Pressure (BP)	X	Х	Х	Х	Х	Х	х

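### MNSI, plasma ROS and leg strength have no scheduled control-phase change, so the primary exercise-versus-control comparison cannot be computed for them

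*Combined protocol and SAP*

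**What the plan says.** Sections 2.1 and 9.1 state the primary objective as a within-person contrast. The trial is to "compare the interventions (exercise versus control phase) in terms of the baseline to follow-up change in the following outcomes: 1) DTI, plasma ROS level", followed by MNSI, oxidative capacity, peak microvascular response, fat-free muscle and leg strength.

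The analysis text is built for that contrast. In 9.3 the change score is the dependent variable, and the model carries "the binary indicator of intervention as a classification factor". Section 9.3.4 adds: "The weight for the control phase will be set to 1 since subjects are not required to exercise". Section 9.3.6 stratifies the exploratory analysis by intervention and then pools the two phases.

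Other text describes a pre/post study. Section 3.2.1 gives the clinical and blood endpoints one assessment before and one after the 10-week programme. In 9.3.2, "the ANCOVA model will include time (baseline versus follow-up) as the within-subject factor of interest". Section 9.3.5 says that groups will not be compared.

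On timing, 6.2.1 says "we will use baseline bloods to estimate levels of hydrogen peroxide as a marker of ROS", meaning the time-0 sample of the glucose tolerance test. Attachment A has a row "Calf muscle performance" marked at weeks 7 and 16 only. Section 4.7.2 mentions a "Post-non-exercise phase visit (section 6.4.3"), but no section in the body says what is done there. The Attachments page says of these documents that "they are not considered part of the protocol".

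**The concern.** A comparison of exercise-phase with control-phase change needs a value at the start of the control phase, one at its end, and values around the exercise phase. If the end-of-control value (MNSI, ROS) or the pre-control value (strength) is never taken, no choice of model or weighting recovers the contrast.

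MNSI is the only symptom outcome named in the primary objective. For MNSI, ROS and strength, the trial could report only an uncontrolled change while its objective promises a controlled one. Measurements missed during the non-exercise period cannot be obtained afterwards.

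**Working it through.** **Inputs.** Attachment A: exercise in weeks 7–16; MNSI weeks 0, 1, 18; bloodwork and OGTT weeks 1, 18; calf muscle performance weeks 7, 16; 9-item performance test weeks 7–16; MRI weeks 1, 5, 18. Section 3.1: a 4-week non-exercise period precedes the programme. Table 2: calf torque on day 2 of exercise weeks 1 and 10, which agrees with Attachment A.

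**Count of scheduled values.**

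| Outcome in 2.1 | Start of control (week ≤ 1) | End of control (weeks 2–6) | Week ≥ 7 | Control-phase changes per person |
|---|---|---|---|---|
| MNSI | 2 | 0 | 1 | 0 |
| Plasma ROS | 1 | 0 | 1 | 0 |
| Leg strength (calf torque) | 0 | 0 | 2 | 0 |
| DTI, 31P, BOLD, IDEAL | 1 | 1 | 1 | 1 |

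The two early MNSI values both precede the non-exercise period, so their difference is not a control-phase change. The 9-item test also starts at week 7. The Biweekly Health Assessment at weeks 3 and 5 has no defined content.

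**Consequence for the 9.3 ANCOVA.** Write C for the control-phase change and E for the exercise-phase change. The model estimates E − C through the coefficient of the intervention indicator. With no C records, the indicator equals 1 on every row, coincides with the intercept, and its coefficient is not identified. The control weight of 1 in 9.3.4 has no records to attach to.

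**What can be computed for MNSI and ROS.** Y(18) − Y(1) = [Y(18) − Y(5)] + [Y(5) − Y(1)] = E + C. That is the sum of the phase changes, where the objective asks for their difference.

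**Non-exercise share of that change.** Week 1 to week 18 is 17 weeks. Exercise takes 10, leaving 17 − 10 = 7, and 7/17 = 41%. Depending on the day within weeks 1 and 18, this runs from 6/16 = 38% to 8/18 = 44%. Part of it falls after the last session (weeks 17–18) rather than in the control phase.

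**Number of outcomes affected.** Counting mitochondrial function and oxidative capacity as one, as hypothesis 2a does, 2.1 names 7: DTI, ROS, MNSI, 31P, BOLD, IDEAL and strength. With three scans (1.2, 3.1, Attachment A), 3 of 7 lack a control-phase change. With two scans (9.3.1, 12.3), the four MRI outcomes lose theirs too: 7 of 7.

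**Does the body fill the gap?** The table of contents lists non-exercise visits (6.4.2) and a post-non-exercise visit (6.4.3). In the body, exercise testing is 6.4.2 (6.4.4 in the contents), the post-exercise visit is 6.4.4 (6.4.6) and the withdrawal visit is 6.4.5 (6.4.7). Each has moved up by two, which fits both control-phase sections having been dropped.

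**Power text in 9.4.** The single-phase figure reproduces. Detectable change = (1.960 + 0.842) × SD/√40, as a percentage of the baseline mean:
- BOLD: 2.802 × 1.26/6.325 = 0.558; 0.558/3.24 = 17.2%
- PCr: 2.802 × 12.85/6.325 = 5.69; 5.69/41.16 = 13.8%
- MNSI: 2.802 × 1.78/6.325 = 0.789; 0.789/5.2 = 15.2%

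All lie within the stated 10–18%. Detectable differences between phases are given for BOLD and PCr only; Table 4 shows NA for the MNSI control change.

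**Utah scale.** Section 3.2.1 lists it among the before-and-after measures. Table 2 has it once (exercise week 1, day 1) and Attachment A has no row for it, so 0 of 40 change scores are scheduled.

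**The case against.** The best counter-reading is that this is a pre/post study whose comparison wording was never cleaned up. Section 9.3.2 carries the title of the primary efficacy analysis and is pre/post; 9.3.5 disclaims a group comparison; the hypotheses in 9.2 are directional statements about exercise with no control, and none concerns leg strength; 3.2.1 asks only for before and after. On that reading, rewording is enough. This is a legitimate way to resolve the conflict, and the fix allows it. It does not remove the conflict, because 2.1, 9.1, 9.3, 9.3.4 and 9.3.6 still promise the phase contrast. It also leaves the MNSI and ROS change spanning non-exercise time.

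Attachment A is not exhaustive: it omits vibration threshold and the Utah scale, marks the 9-item test weekly where Table 2 has it twice, and is kept outside the protocol. A missing mark is therefore weaker evidence than an explicit statement. But 3.2.1 and Table 2 independently give two values, and nothing in the body supplies a third.

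Three smaller points stand in part. The 41% is a schedule figure: the nominal 4 + 10 weeks would give 4/14 = 29%, and 4.7.2 tolerates up to three months between blood draw and the post-non-exercise visit, so individual shares will vary more widely than 38–44%. The NA in Table 4 describes preliminary data and shows only that the MNSI phase contrast was not powered. Table 2 is introduced as a brief overview, so the second Utah assessment may be intended though unscheduled.

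**Conclusion.** The concern holds. As scheduled, the exercise-versus-control comparison cannot be computed for MNSI, plasma ROS or leg strength: 3 of 7 primary outcomes, with 0 of 40 control-phase changes each. It is 7 of 7 if only two scans are done. The 9.3.2 analysis remains available for all three, but it is uncontrolled, and for MNSI and ROS it cannot isolate the exercise period.

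This rests on Attachment A and Table 2 being the operative schedule and on there being no assessment the documents leave unmentioned. It does not depend on the power calculation. It needs resolving because a primary objective and its analysis model refer to data that the plan does not collect.

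**What to change.** State the end-of-control assessments in the body of section 6.4 as well as in Attachment A, restoring the visit that 4.7.2 refers to. Then, by outcome:

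- **MNSI:** add it at the existing week-5 MRI visit.
- **ROS:** either add one fasting sample at week 5, or restate 2.1 and 9.1 so that ROS is pre/post only.
- **Leg strength:** either measure calf torque at week 0 or 1 and again before the first exercise session (a week-5 value alone is not enough), or restate it as an exercise-phase pre/post outcome with no control comparison.
- **Utah scale:** add it at the week-18 visit.
- **MRI:** reconcile three scans (1.2, 3.1, Attachment A) with two (9.3.1, 12.3).
- **Analysis:** for any outcome left pre/post only, say that the 9.3 ANCOVA does not apply and that 9.3.2 is its analysis, and bring 9.3.5 into line.

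Cost: MNSI and the Utah scale use existing instruments and visits. ROS needs one extra draw and assay per participant, 40 in total if all can still be measured. Strength needs up to two extra torque tests per participant. The documents do not give enrolment status; for anyone already past week 5, only the rewording is open. If nothing is added for ROS or strength, the cost is wording in 2.1, 9.1 and 9.3 and a narrower claim.
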